10.1.6.5 Publication Authorship Requirements

Authorship for any Otsuka-sponsored publications resulting from the conduct of this trial will be based on International Committee of Medical Journal Editors (ICMJE) authorship criteria (<http://www.icmje.org/recommendations>). According to ICMJE guidelines, one may be considered an author only if the following criteria are met:

- 1) Substantial contributions to the conception or design of the work; or the acquisition, analysis, or interpretation of data for the work; AND
- 2) Drafting the work or revising it critically for important intellectual content; AND
- 3) Final approval of the version to be published; AND
- 4) Agreement to be accountable for all aspects of the work in ensuring that questions related to the accuracy or integrity of any part of the work are appropriately investigated and resolved.

All authors must meet the above criteria, and all who qualify for authorship based on the above criteria should be listed as authors.

Investigators or other trial subjects who do not qualify for authorship may be acknowledged in publications resulting from the trial. By agreeing to participate in the trial, investigators or other trial subjects consent to such acknowledgement in any publications resulting from its conduct.

10.2 Appendix 2: Clinical Laboratory Tests

The tests detailed in Table 10.2-1 will be performed.

Table 10.2-1 Clinical Laboratory Assessments	
Hematology: HbA1c Hemoglobin Hematocrit MCH MCHC MCV Platelet count RBC count RBC morphology RDW WBC count with differential Urinalysis: Specimen Appearance Color Occult Blood Glucose Microscopic analysis, WBC/RBC counts per high powered field pH Protein Specific Gravity Ketones Urine Drug Screens: Amphetamines/MDMA Barbiturates Benzodiazepines Cannabinoids Cocaine Methadone Opiates Phencyclidine Propoxyphene Drug and Alcohol Screening: Blood alcohol	Serum Chemistry: ALP ALT AST Bilirubin, total BUN Calcium Cholesterol (total, LDL, and HDL) CPK Creatinine GGT Glucose LDH Magnesium Potassium Prolactin Protein, total Sodium Triglycerides Uric acid Additional Tests: Urine and serum pregnancy for FOCBP ^a

ALP = alkaline phosphatase; BUN = blood urea nitrogen; GGT = gamma glutamyl transferase; HDL = high-density lipoprotein; LDH = lactic dehydrogenase; LDL = low-density lipoprotein; MCH = mean corpuscular hemoglobin; MCHC = mean corpuscular hemoglobin concentration; MCV = mean corpuscular volume; MDMA = methylenedioxymethamphetamine; RBC = red blood cell; RDW = red cell distribution width; WBC = white blood cell.

^aAll positive urine pregnancy test results must be confirmed by a serum test. Subjects with a positive serum pregnancy test result at screening/baseline must not be enrolled and subjects with a positive serum pregnancy test result during the trial must discontinue treatment and be withdrawn from the trial.

10.3 Appendix 3: Contraceptive Guidance and Collection of Pregnancy Information

Females of childbearing potential are females whose menstruation has started and who are not documented as sterile (eg, have had a bilateral oophorectomy, or hysterectomy, or who have been postmenopausal for at least 12 months).

For males and FOCBP, who are sexually active, there must be a documented agreement that the subject and their partner will take effective measures (ie, 2 different approved methods of birth control or remains abstinent) to prevent pregnancy during the course of the trial and for 30 days after the last dose of IMP. Unless the subject is sterile (ie, females who have had a bilateral oophorectomy, have had a hysterectomy, or have been postmenopausal for at least 12 consecutive months; or males who have had a bilateral orchiectomy) or remains abstinent during the trial and for 30 days after the last dose of IMP, 2 of the following approved methods of birth control must be used: vasectomy, tubal ligation, intrauterine device, birth control pills, birth control implant, birth control depot injection, condom with spermicide, sponge with spermicide, or occlusive cap (vaginal diaphragm or cervical/vault cap) with spermicide. Any single method of birth control, including vasectomy and tubal ligation, may fail, leading to pregnancy. The contraceptive method will be documented in eSource. Abstinence is defined as refraining from heterosexual intercourse during the entire period of risk associated with the trial treatments. The reliability of sexual abstinence should be evaluated in relation to the duration of the clinical trial and the preferred and usual lifestyle of the subject.

Consensual sexual activity that cannot biologically result in pregnancy may not be subject to required birth control methods, following discussion with the medical monitor. Male subjects must also agree not to donate sperm from trial screening/baseline through 30 days after the last dose of IMP.

Before enrolling males and females in this clinical trial, investigators must review the below information about trial participation as part of the ICF process. The topics should generally include:

- General information
- Informed consent form
- Pregnancy prevention information
- Drug interactions with hormonal contraceptives
- Contraceptives in current use
- Follow-up of a reported pregnancy

Before trial enrollment, males and FOCBP must be advised of the importance of avoiding pregnancy during trial participation and the potential risk factors for an unintentional pregnancy. Subjects must sign the ICF confirming that the above-mentioned risk factors and the consequences were discussed.

A urine or serum pregnancy test for human chorionic gonadotropin will be performed at screening/baseline and at each check-in to the inpatient facility on all FOCBP. If a urine test is performed and is positive, the investigator will follow-up with a confirmatory serum test.

During the trial, all FOCBP should be instructed to contact the investigator immediately if they suspect they might be pregnant (eg, missed or late menstrual cycle). Male subjects must be instructed to contact the investigator immediately, during the trial, if their partner suspects that they might be pregnant (eg, missed or late menstrual cycle).

If a subject is suspected to be pregnant before she receives IMP, the IMP administration must be withheld until the results of serum pregnancy tests are available. If the pregnancy is confirmed, the subject must not receive the IMP and must not be enrolled in the trial. If pregnancy is suspected while the subject is taking IMP, the IMP must be withheld immediately (if reasonable, taking into consideration any potential withdrawal risks) until the result of the pregnancy test is known. If pregnancy is confirmed, the IMP will be permanently discontinued in an appropriate manner (eg, dose tapering if necessary for subject safety) and the subject will be withdrawn from the trial. Exceptions to trial discontinuation may be considered for life-threatening conditions only after consultations with the IRE contact (see the title page of this protocol for contact information).

The investigator must immediately notify the sponsor (within 24 hours) of any pregnancy associated with IMP exposure during the trial and for at least 30 days after the last dose of IMP, and record the event on the IRE form and forward it to the sponsor. The sponsor will forward the Pregnancy Surveillance Form(s) to the investigator for monitoring the outcome of the pregnancy.

Protocol required procedures for trial discontinuation and follow-up must be performed on the subject unless contraindicated by pregnancy (eg, x-ray studies). Other appropriate pregnancy follow-up procedures should be considered if indicated. In addition, the investigator must report to the sponsor, on the Pregnancy Surveillance Form(s), follow-up information regarding the course of the pregnancy, including perinatal and neonatal outcome. Infants will be followed for a minimum of 6 months from the date of birth.

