Assessments for Safety: Adverse event (AE) reporting, clinical laboratory tests (including prolactin and glycosylated hemoglobin [HbA1c]), electrocardiogram (ECG), vital signs, physical examination, Simpson Angus Scale (SAS), Abnormal Involuntary Movement Scale (AIMS), Barnes Akathisia Rating Scale (BARS), and Columbia-Suicide Severity Rating Scale (C-SSRS).

Screening/Other: Medical, psychiatric, and medication history; urine drug and blood alcohol screening; and urine pregnancy test.

Data Monitoring Committee: None.

Statistical Methods:

The sample size is not based on statistical power considerations but on the number of subjects rolling over from the lead-in trials. The trial population will be derived from eligible subjects who completed the previous double-blind brexpiprazole BPD trials. The number of eligible subjects will be limited by the number of subjects enrolled into the double-blind trials.

The primary safety analysis is the frequency and severity of AEs in the open-label treatment phase. All AEs will be coded by system organ class and the Medical Dictionary for Regulatory Activities preferred term. The incidence of the following events will be summarized by the prior treatment group:

- 1) Treatment-emergent adverse events (TEAEs)
- 2) TEAEs by severity,
- 3) TEAEs potentially causally related to the IMP,
- 4) TEAEs with an outcome of death,
- 5) Serious TEAEs,
- 6) TEAEs leading to discontinuation of the IMP,
- 7) Adverse events of special interest (AESI).

A TEAE is defined as an AE that starts after the first dose of IMP or an AE that is reported at baseline and increases in intensity or becomes serious or IMP-related or results in death, discontinuation, interruption or reduction of IMP. Information about new onset or exacerbation of “Pathological Gambling and Other Compulsive Behaviors” will be collected and analyzed as an AE of special interest.

Complete details of the planned statistical analysis will be presented in the statistical analysis plan.

[figure not shown]
Trial Duration:

Each subject in this trial is expected to participate in the following periods of the trial (approximate durations listed), for approximately 15 weeks:

- Eligibility screening period (1 day) (If a subject is unable to rollover immediately, up to 3 days may be permitted between the end of the double-blind trial and the start of IMP in the open-label extension trial; however, this must be discussed with the medical monitor.)

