6.5 Concomitant Medications or Therapies

The investigator will record all medications and therapies taken by the subject from the screening/baseline visit through the end of the evaluation period (defined as the time period during which subjects are evaluated for primary and/or secondary objectives) in eSource. The investigator will also record all medications and therapies taken by the subject for treatment of an AE or which caused an AE until the end of the trial (defined as the last date of contact or date of final contact attempt) in eSource.

For concomitant medications, the following will be recorded in eSource: medication, indication, dose, frequency, route, start date, and end date. For concomitant therapy, the following will be recorded in eSource: therapy, indication, start date, end date, and frequency.

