A pregnancy test will be conducted in FOCBP (refer to [Section 10.3](#) for definition) prior to trial intervention; results must be available prior to the administration of the IMP.

Pregnancy tests can be performed at any point during the trial if pregnancy is suspected.

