8.8.3 Immediately Reportable Events

The investigator must immediately report (within 24 hours), using an IRE form, after he/she or site personnel become aware of any IRE (SAE, AE related to occupational exposure, AESI, potential serious hepatotoxicity, or confirmed pregnancy), by telephone, fax, or e-mail to the sponsor or designee using the contact information on the cover page of this protocol (Please note that the IRE form is NOT the AE page in eSource.).

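### Exposed pregnancies must be notified for at least 30 days after the last dose, but scheduled contact and the protocol's instructions to report stop at about Day 21, leaving the last 6 to 12 days to chance

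*Protocol*

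**What the plan says.** **The duty.** Protocol Section 10.3 sets a 24-hour limit for telling the sponsor about "any pregnancy associated with IMP exposure during the trial and for at least 30 days after the last dose of IMP". Exclusion criterion 1 and Section 10.3 apply the same 30 days to contraception and sperm donation. Section 8.8.3 counts pregnancy among the immediately reportable events (IREs), listing "AE related to occupational exposure, AESI, potential serious hepatotoxicity, or confirmed pregnancy" after serious adverse events. Section 8.8.1 includes partner pregnancies and notes that a normal pregnancy is not an adverse event.

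**The means of finding out.**
- Section 8.8.8.2 requires active IRE monitoring up to 21 (±3) days after the last dose. Footnote q of Table 1.3-1 collects IREs through the last trial contact.
- For women of childbearing potential (FOCBP), Section 10.3 says: "During the trial, all FOCBP should be instructed to contact the investigator immediately if they suspect they might be pregnant".
- For men it says: "Male subjects must be instructed to contact the investigator immediately, during the trial, if their partner suspects that they might be pregnant".
- On testing, Section 8.7.1 says: "Pregnancy tests can be performed at any point during the trial if pregnancy is suspected". Footnote n of Table 1.3-1 says the same.
- Section 10.3 adds that a pregnancy test "will be performed at screening/baseline and at each check-in to the inpatient facility on all FOCBP". Table 1.3-1 schedules urine tests at baseline and Weeks 4, 8 and 12/ET, and none at the follow-up contact.

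**The concern.** The sponsor has set 30 days as its pregnancy window, for both prevention and reporting. A reporting duty only works if the site learns of the event, and the stated means of learning stop before the window does. A woman who conceives around or after the last dose may test negative at Week 12 and first suspect a pregnancy after the Day 21 contact. A male subject may hear of a partner's pregnancy at the same late stage. Nothing in the protocol text then tells either of them to call.

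If the site never hears, the Pregnancy Surveillance Forms and the infant follow-up of at least 6 months in Section 10.3 do not start. What is at stake is therefore participant and infant safety information, not an efficacy or adverse event estimate.

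**Working it through.** No power or sample size figure bears on this. The check is day arithmetic and a comparison of texts.

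**Inputs.** Notification window: 30 days after the last dose (10.3). Last scheduled contact: Day 21 ± 3 (Table 1.3-1, 4.1, 8.8.8.2). Treatment: 12 weeks.

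**1. Days with no scheduled contact** = 30 − day of the last contact.
- Earliest contact: 21 − 3 = 18, so 30 − 18 = 12 days (12/30 = 40%).
- Nominal contact: 30 − 21 = 9 days (9/30 = 30%).
- Latest contact: 21 + 3 = 24, so 30 − 24 = 6 days (6/30 = 20%).

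**2. Does *during the trial* reach Day 30 for a given subject?** The Synopsis has each subject "expected to participate in the following periods of the trial (approximate durations listed), for approximately 15 weeks". That figure reproduces: 12 × 7 = 84 days of treatment, 84 + 21 = 105 days, 105/7 = 15.0 weeks. Participation therefore ends at the Day 21 contact. The 10.3 duty runs to 84 + 30 = 114 days, 114/7 = 16.3 weeks. Two further texts point the same way. Section 6.5 records treatment of adverse events "until the end of the trial (defined as the last date of contact or date of final contact attempt", which is tied to contact with the subject. Section 10.3 itself names the trial and the 30 days after the last dose as separate spans. On this reading the call-in instructions and testing on suspicion lapse at the last contact.

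**3. Are the days before that contact covered?** Yes. Pregnancy is an IRE (8.8.1), IREs are actively monitored up to the contact (8.8.8.2), and footnote q collects them there. The call-in instructions and testing on suspicion are also in force.

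**4. What remains after the contact?** Section 8.8.8.3 accepts new IREs that reach the investigator later, so a route exists. It is passive, and the protocol does not tell subjects to use it.

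**5. The testing sentence.** Inclusion criterion 2 admits outpatients, and Section 4.1 describes no inpatient stay. The inpatient check-in in 10.3 therefore never occurs, and Table 1.3-1 holds the actual test schedule.

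**The case against.** The strongest reply is that the system is adequate as written. The 30-day duty is clear, any confirmed pregnancy the site learns of is reportable within 24 hours, Section 8.8.8.2 sends readers to 10.3 for pregnancy, and late reports are accepted. This stands: the reporting rule is sound, and a reader who inferred that 10.3 and 8.8.8.2 contradict each other would be wrong. One sets a duty to report, the other a period of active monitoring. The weakness is only in how late cases come to light.

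The wording of the instructions can also be contested. Section 4.4 defines the end of trial by the last subject's final contact, which would stretch *during the trial* past Day 30 for most subjects. The sentence for FOCBP may fix when the instruction is given, not when she should call. Both readings are possible. The first still fails for the last subjects, and no subject can know when that date falls. The second is not open for men, where the phrase attaches to the call itself. The consent form may also say more than the protocol, and that could not be checked.

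Two stronger readings are tempting, and the documents do not support them:
- *That the first 18 to 24 days are also a gap, because the follow-up column lists only adverse events and concomitant therapy and the scripted prompt is general.* Step 3 shows that pregnancy is assigned to that contact. A specific question would help, but its absence is not an error.
- *That Section 8.8.8.3 puts a causality filter on pregnancies.* Its condition applies to new IREs occurring after the last scheduled contact. A pregnancy that began earlier is outside it, and 8.8.8.2 refers pregnancy to 10.3, which is framed by exposure.

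**Conclusion.** The point holds in a narrow form and is minor. For the last 6 to 12 days of the 30-day window (nominally 9), the protocol provides no scheduled contact and no instruction to subjects to report a pregnancy, although it obliges the investigator to report one. The inpatient check-in wording is a separate drafting error in the same section.

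This rests on the per-subject reading of *during the trial*, which is the natural one but not the only one, and on the protocol text alone. The documents give neither the number of FOCBP nor a pregnancy rate, so no case count can be derived. Few cases are to be expected, given the required contraception and the short interval. The adverse event analysis is unaffected.

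**What to change.** 1. In Section 10.3, extend both self-report instructions (women, and men about partners) to cover the trial and the 30 days after the last dose.
2. Extend the permission to test on suspicion (8.7.1 and footnote n of Table 1.3-1) to the same 30 days.
3. At the existing Day 21 (±3) contact, ask about pregnancy in the subject or partner, and remind subjects to call through Day 30.
4. In footnote q, state that pregnancies are reported through at least 30 days after the last dose, as 10.3 requires.
5. In 10.3, replace the inpatient check-in phrase with a reference to the visits in Table 1.3-1.

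The cost is one question at a contact that already takes place, an occasional test on suspicion, and a minor edit to the protocol and consent form. No contact is added or moved, and the SAP does not change.

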10.4 Appendix 4: Abbreviations

Abbreviation	Definition
5-HT	Serotonin
AAD	Agitation in Alzheimer's dementia
ADHD	Attention-deficit/hyperactivity disorder
ADT	Antidepressant therapy
AE	Adverse event
AESI	Adverse event of special interest
AIMS	Abnormal Involuntary Movement Scale
ALP	Alkaline phosphatase
ALT (SGPT)	Alanine aminotransferase (serum glutamic-pyruvic transaminase)
AST (SGOT)	Aspartate aminotransferase (serum glutamic-oxaloacetic transaminase)
BARS	Barnes Akathisia Rating Scale
BPD	Borderline personality disorder
bpm	Beats per minute
BUN	Blood urea nitrogen
CCI	[REDACTED]
CCI	[REDACTED]
COVID-19	Coronavirus disease of 2019
CPK	Creatine phosphatase
C-SSRS	Columbia-Suicide Severity Rating Scale
CYP	Cytochrome P450
D	Dopamine
DBP	Diastolic blood pressure
DSM-IV	Diagnostic and Statistical Manual of Mental Disorders, 4th edition
ECG	Electrocardiogram
eICF	Electronic informed consent
EPS	Extrapyramidal symptoms
ET	Early termination
FDA	Food and Drug Administration
FOCBP	Females of childbearing potential
GCP	Good Clinical Practice
GGT	Gamma glutamyl transferase
CCI	[REDACTED]
HbA1c	Glycosylated hemoglobin
HDL	High-density lipoprotein
IB	Investigator's Brochure
ICF	Informed consent form
ICH	International Council for Harmonisation
ICMJE	International Committee of Medical Journal Editors
ID	Identifier
IEC	Independent ethics committee
IMP	Investigational medicinal product
IND	Investigational New Drug

Abbreviation	Definition
IRB	Institutional review board
IRE	Immediately reportable event
K _i	Inhibition constant
LDH	Lactic dehydrogenase
LDL	Low-density lipoprotein
LOCF	Last observation carried forward
MCH	Mean corpuscular hemoglobin
MCHC	Mean corpuscular hemoglobin concentration
MCV	Mean corpuscular volume
MDD	Major depressive disorder
MDMA	Methylenedioxymethamphetamine
OC	Observed cases
PD	Pharmacodynamic
CCI	[REDACTED]
PK	Pharmacokinetic
PQC	Product quality complaint
PTSD	Post-traumatic stress disorder
QTc	Corrected QT interval
QTcB	QT interval corrected for heart rate using Bazett's formula
QTcF	QT interval corrected for heart rate using Fridericia's formula
QTcN	QT interval corrected for heart rate using the Food and Drug Administration Neuropharm Division formula
RBC	Red blood cell
RDW	Red cell distribution width
SAE	Serious adverse event
SAP	Statistical analysis plan
SAS	Simpson Angus Scale
SBP	Systolic blood pressure
SYE	Subject years of exposure
TEAE	Treatment-emergent adverse event
ULN	Upper limit of normal
US	United States
WBC	White blood cell
CCI	[REDACTED]
CCI	[REDACTED]

10.5 Appendix 5: Criteria for Identifying Laboratory Values of Potential Clinical Relevance

Laboratory Tests	Criteria
Chemistry	
AST (SGOT)	$\geq 3 \times \text{ULN}$
ALT (SGPT)	$\geq 3 \times \text{ULN}$
Alkaline phosphatase	$\geq 3 \times \text{ULN}$
Lactate dehydrogenase	$\geq 3 \times \text{ULN}$
Blood urea nitrogen	$\geq 30 \text{ mg/dL}$
Creatinine	$\geq 2.0 \text{ mg/dL}$
Uric acid	
Men	$\geq 10.5 \text{ mg/dL}$
Women	$\geq 8.5 \text{ mg/dL}$
Bilirubin (total)	$\geq 2.0 \text{ mg/dL}$
Creatine phosphokinase	$> 3 \times \text{ULN}$
Prolactin	$> \text{ULN}$
Hematology	
Hematocrit	
Men	$\leq 37\% \text{ and decrease of } \geq 3 \text{ percentage points from baseline}$
Women	$\leq 32\% \text{ and decrease of } \geq 3 \text{ percentage points from baseline}$
Hemoglobin	
Men	$\leq 11.5 \text{ g/dL}$
Women	$\leq 9.5 \text{ g/dL}$
WBC count	$\leq 2,800 \text{ mm}^3 \text{ or } \geq 16,000 \text{ mm}^3$
Eosinophils	$\geq 10\%$
Neutrophils	$\leq 15\%$
Absolute neutrophil count	$\leq 1,500/\text{mm}^3$
Platelet count	$\leq 75,000/\text{mm}^3 \text{ or } \geq 700,000/\text{mm}^3$
Urinalysis	
Protein	Increase of ≥ 2 units
Glucose	Increase of ≥ 2 units
Casts	Increase of ≥ 2 units
Additional Criteria	
Chloride	$\leq 90 \text{ mEq/L} \text{ or } \geq 118 \text{ mEq/L}$
Potassium	$\leq 2.5 \text{ mEq/L} \text{ or } \geq 6.5 \text{ mEq/L}$
Sodium	$\leq 126 \text{ mEq/L} \text{ or } \geq 156 \text{ mEq/L}$
Calcium	$\leq 8.2 \text{ mg/dL} \text{ or } \geq 12 \text{ mg/dL}$
Glucose	
Fasting	$\geq 100 \text{ mg/dL}$
Nonfasting	$\geq 200 \text{ mg/dL}$
Total cholesterol, fasting	$\geq 240 \text{ mg/dL}$
LDL cholesterol, fasting	$\geq 160 \text{ mg/dL}$
HDL cholesterol, fasting	
Men	$< 40 \text{ mg/dL}$
Women	$< 50 \text{ mg/dL}$
Triglycerides, fasting	$\geq 150 \text{ mg/dL}$

